#### 6.1 Statistical software

The R programming environment will be primarily used for analysis.

## 6.2 Assumption checking

Data will be assessed for normality via q-q plots, histogram (visually) and Shapiro-Wilk tests. For normal and non-normal data, appropriate tests will be applied (e.g. Wilcoxon or Student's t test).

## 6.3 General study characteristics

Summary statistics on general study data, including dropout rate, compliance, and signup rate, will be summarised and can be presented in the manuscript text or participant flowchart.

# 6.4 Epigenetic data

#### 6.4.1 Quality control

Samples from the same participant and sample type will be processed as much as possible on the same Illumina Methylation EPIC beadchip (n=8 samples per beadchip), but timepoint position will be randomised on the array to minimise batch effects. DNA methylation data quality control and preprocessing will be performed using a standardised process in the [name] group. The R packages minfi, ChAMP, and ENmix will be used for preprocessing. Briefly, any samples not below a median unmethylated or methylated intensity threshold will be excluded from analysis. Probes that fail the detection p threshold (p <0.01) will be excluded from the dataset. Samples that have more than 10% failed probes will be excluded from the dataset. Beta value distributions will be visualised and outliers identified (for each sample type). Dye bias correction and BMIQ normalisation will be conducted. In addition, control probes will be visualised to check for efficiency of bisulfite conversion, for instance. An amended version of the preprocessing pipeline may be utilised if ongoing experiments demonstrated improvements in reproducibility and noise.

Potential sample mix-ups will be checked by extracting information on control single nucleotide polymorphism (SNP) probes present on the EPIC array. Obvious discrepancies will be further investigated and samples may need to be excluded.

As part of quality control, sample principal components will be checked for association with age, immune cell composition, processing date, beadchip, and other potential biological and technical effects to evaluate batch effects. These will be visualised by correlation heatmaps for the first 10 principal components and principal component and uniform manifold approximation and projection (UMAP) plots. If significant non-biological batch effects are found (e.g. processing day, beadchip), these may be corrected using the ComBat function within the ChAMP R package. As part of quality control, we will also investigate correlation of WID general age with chronological age.

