#### 6.4.3 Primary endpoint reporting

For primary endpoint analysis, paired Wilcoxon tests will be performed on adjusted WID scores associated with disease risk, cellular ageing, or exposure, in cervical samples at baseline and month 6 of the intervention (adjusted for immune cell composition). For visualisation, points and lines may be coloured by compliance score, delta BMI, or smoking status at the end of the intervention. Data will be visualised using Spaghetti plots and may additionally be visualised using violin/box plots with overlayed jitter plots.

Analyses will be presented separately per sub-study and a comparison between the two randomised arms in the diet intervention study may be conducted. The analysis is predominantly conducted ITT, but separate subgroup analyses may be conducted as follows:

- $\bullet$  per protocol, if at least 30 individuals have a cumulative compliance score of more than 80%
- diet intervention: timing of fasting, breakfast versus dinner cancellation

Mixed-effects models could provide a complimentary method of reporting individual effects over time.

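### Section 6.4.1 states the array intensity filter in the wrong direction, so as worded it drops adequate arrays and passes low-intensity ones

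*SAP*

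**What the plan says.** Section 6.4.1 of the SAP summarises the preprocessing of the methylation arrays. It refers to a standardised process run with named R packages and then lists the main steps. The first exclusion step is on signal intensity: "any samples not below a median unmethylated or methylated intensity threshold will be excluded from analysis".

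Two further exclusion rules follow directly. At probe level: "Probes that fail the detection p threshold (p <0.01) will be excluded from the dataset". At sample level: "Samples that have more than 10% failed probes will be excluded from the dataset". The paragraph then provides for a visual check of the beta-value distributions, with identification of outliers, and for a check of control probes. It ends by allowing some flexibility: "An amended version of the preprocessing pipeline may be utilised if ongoing experiments demonstrated improvements in reproducibility and noise".

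Section 6.4.3 defines the primary analysis as paired Wilcoxon tests on adjusted scores from cervical samples at baseline and month 6. The samples that survive Section 6.4.1 are the input to those tests.

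**The concern.** An intensity filter in a quality-control step is there to remove arrays whose signal is too weak to trust. The sentence in Section 6.4.1 does the opposite: it excludes the samples that reach the threshold and leaves in those that fall short of it.

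This is an operative rule, not background text. A participant contributes to the primary paired test only if both her baseline and her month 6 cervical sample are retained. An analyst who followed the sentence as written would build the wrong dataset. An analyst who did what was presumably meant would depart from the written plan, and Section 1 requires deviations to be described and justified.

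**Working it through.** The SAP gives no figure to reproduce on this point, and the check needs no arithmetic. It is a reading of the rule against its alternatives and its neighbours.

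**Inputs**
- The intensity rule, from Section 6.4.1, quoted above.
- The threshold, described only as "a median unmethylated or methylated intensity threshold". No value is given. Call it T, and allow it to differ between the methylated and unmethylated channels.
- The two neighbouring exclusion rules in the same paragraph.
- The primary analysis in Section 6.4.3.

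**Step 1. Direction.** Not below T is the same as at or above T. The rule excludes that set, so the samples it keeps are those below T.

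**Step 2. Two channels.** The sentence names two channels joined by *or*, so the negation can be read in two ways:
- Reading A: exclude if either channel is at or above its threshold.
- Reading B: exclude unless at least one channel is below its threshold, that is, exclude if both are at or above.

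A low-signal filter would exclude a sample if either channel is below its threshold.

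| Sample | As written, reading A | As written, reading B | Low-signal filter |
|---|---|---|---|
| Both channels at or above T | excluded | excluded | kept |
| One channel below T | excluded | kept | excluded |
| Both channels below T | kept | kept | excluded |

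Under both readings the first and third rows are reversed: the sound array goes and the array weak in both channels stays. Under reading B the written rule is the exact complement of a low-signal filter. The readings differ only for samples weak in one channel. None of this depends on the value of T.

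**Step 3. Context.** The next two rules discard probes that fail detection and samples with too many failed probes. Both remove poor signal. Nothing in the SAP describes the intensity threshold as an upper limit, for example for saturation, which is the one reading under which the written direction would make sense.

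**Step 4. Correction elsewhere.** No other section restates the intensity rule. The provision for an amended pipeline concerns gains in reproducibility and noise and says nothing about the direction of this filter.

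**Step 5. What the other checks recover.** The limit of 10% failed probes may remove some of the low-intensity arrays that the written rule lets through, and the outlier and control-probe checks may flag others. None of these steps can restore an adequate array that the intensity rule has already excluded.

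**The case against.** The strongest reply is that this is a slip of the pen: a stray negation, or *below* written for *above*. The sentence is part of a brief summary of an established laboratory process, its neighbours make the purpose plain, and nobody running a methylation study would discard the arrays that worked. Most of that stands. The pipeline code is not before us and may be correct, and the literal rule is unlikely ever to be run. It lowers the weight of the point but does not make the sentence right, and the SAP is the document against which the reported exclusions will be compared.

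Three stronger readings are tempting, and the document does not support them.

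- A reader might infer that the primary analysis will lose nearly all its samples. If one assumes that 95% to 99% of arrays reach the threshold, the literal rule excludes that same 95% to 99%. But that range is an assumption with no basis in the SAP, and it only restates the literal reading. It does not estimate what is likely to happen.
- A reader might infer that failed arrays will be analysed. That follows from the intensity rule alone. The failed-probe rule and the outlier and control-probe checks stand beside it and could still remove or flag some of those arrays.
- A reader might treat the missing threshold value, or the question of one channel or both, as separate errors. The SAP leaves such detail to the standard process, and *or* is ordinarily read as either channel being enough. These are matters of detail that the corrected sentence can settle in passing.

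It is also fair to say that Section 1 already covers an open correction, because it requires deviations to be described and justified. The difficulty arises only if the rule is reinterpreted silently.

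**Conclusion.** The point holds as an error of wording in an operative rule. Section 6.4.1 states the sample intensity filter in reverse, nothing else in the SAP puts it right, and the rule is one of several that decide which samples enter the primary paired analysis. The conclusion rests on one assumption: that low intensity is the failure direction. The neighbouring rules support this and nothing in the SAP contradicts it.

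The size cannot be given as a number of samples, because the SAP states neither a threshold nor a pass rate. If the code follows the usual purpose of such a filter, the results are unaffected and only the written plan is wrong. If the sentence were applied literally, the set of retained samples would be wrong. The first is much the more likely. The sentence should be corrected, but it gives no ground for doubting the rest of the preprocessing plan.

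**What to change.** Replace the sentence in Section 6.4.1 with one that says: exclude a sample if its median methylated intensity or its median unmethylated intensity is below the threshold. Worded this way, it also makes clear that one weak channel is enough. Before issuing the change, the sponsor should confirm that the standard pipeline applies the rule in this direction and on either channel.

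Adding the pipeline's numerical threshold is optional. It would match the neighbouring rules, which give theirs (p < 0.01 and 10%).

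The cost is one sentence in the SAP and a check of the code. The design, the sample size and the data collection do not change. If the analysis has already been run, a line in the report stating the direction actually applied would serve the same purpose under the deviation rule in Section 1.

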#### 6.4.2 Exploratory analysis

Initial data exploration will assess the association of cancer risk- and age-associated signature scores with immune cell composition. DNAme signature scores of interest highlighted above (e.g. but not limited to WID-BC, WID-OC, WID-EC, WID-CIN, WID-REA, WID-SOLA) at month 0 will be visualised as follows:

- chronological age
- immune cell composition (ic)
- BMI
- smoking status

for each tissue, amongst other molecular and cellular analyses. It is assumed that epigenetic indices should be corrected for immune cell composition (for blood: myeloid fraction, consisting of monocyte, eosinophil and neutrophil composition) using baseline values for all participants in a given study arm.

To investigate longitudinal effects, spaghetti plots will be generated for all timepoints (baseline, M2, M4, M6; adjusted for age (across groups) and immune cell composition (ic)), grouping or colouring by the following variables:

- compliance score (colour gradient), separate for each intervention (smoking cessation, intermittent fasting with ketogenic supplement, intermittent fasting without ketogenic supplement)
- smoking status at the end of the intervention (smoking cessation only)
- delta BMI month 6 and month 0 (colour gradient) (intermittent fasting only)
- average  $\beta$ -hydroxy butyrate value (colour gradient) (subgroup of intermittent fasting only)

The suitability of random intercepts and slopes will also be explored during exploratory analysis. Individual slopes for scores will be plotted against covariates.

In addition to visualisation, summary tables (median and standard deviation) will be generated per group per timepoint, assessing cross-sectional (between groups) and longitudinal differences (within subjects), stratifying median compliance score.

To evaluate potential associations between changes in epigenetic scores and clinical or other factors, visualisation plots may be generated and covariate adjustment may be conducted for primary and secondary analyses, where appropriate.

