# 6 Analysis

Analyses will be conducted and reported separately per sub-study (i.e. smoking cessation and intermittent fasting) after all samples for the month 6 timepoint have been collected. Key analyses will be performed on the ITT population. A per-protocol analysis will be conducted if sufficient individuals are available with above 80% compliance (n=30), or alternatively and additionally a subgroup analyses split by median compliance score (above and beyond, respectively). Descriptive statistics of dynamics over 6 months without an intervention will be reported and if sufficient individuals are present per study arm (n  $\geq 10$ ) that did not adhere, these may be used as a nested control group; although this number is small, it could be informative for dynamic changes without intervention.

The longitudinal manner of data collection enables baseline-controlled pairwise comparison (paired t or Wilcoxon test) for each participant at baseline and after 6 months; linear mixed effects-models may also be employed. Longitudinal dynamics and repeated measurements per participant, evaluating data from baseline, 2, 4, and 6 months, will be assessed using linear (or non-linear) mixed-effects models to account for inter-individual heterogeneity and differences in response (random intercept and slopes, if appropriate). In the intermittent fasting group, cross-sectional analyses may be used to compare effects for use with and without ketogenic supplement. Change from baseline may be reported in a descriptive manner.

Methylation data will be adjusted for sample cell type composition which is known to influence methylation levels. Many of the assessed factors are influenced by age. Dependence on other, non-intervention related covariates will be investigated during the exploratory data visualisation and assessment, and factors may be associated as covariates in mixed-effects models if necessary.

If a number of participants does not adhere to the intervention but continues to provide samples and the assumption of common support holds, we may be able to explore the average treatment effect (ATE) and causal average treatment effect (CATE) using causal inference (g methods) via covariate adjustment for selected secondary outcomes (in particular longitudinal DNA methylation analyses).

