#### 6.4.4 Secondary endpoint reporting

To investigate the magnitude and temporal dynamics of changes in methylation indices for each surrogate tissue, namely cervical, buccal, and blood, linear mixed-effects models will be estimated, combining tissues where applicable. The use of random slopes and intercepts will be explored (R package lme4 or nlme, lmer function). Compliance score, sample cell composition, BMI, smoking status, or other factors identified during exploratory data analysis may be used as covariates. Additionally, in a descriptive manner, the change from baseline will be reported within each tissue and paired comparisons will be carried out. Examples of linear models (covariates may be altered or extended) are provided below:

$$model_{intermittent \ fasting} = lmer(score \sim compliance + sample \ type + BMI + ic + age_{baseline} + (time|id), data = data)$$
(1)

$$model_{smoking \ cessation} = glmer(score \sim compliance + sample \ type + smoking \ status + ic + age_{baseline} + (time|id), data = data)$$
(2)

Separate models per sample type may be even more informative, this will be explored during exploratory data analysis.

Using models based on equations in equations 1 and 2, the data will be characterised as follows:

- 1. Estimation of average changes in all participants
- 2. Estimation of changes for individual participants
- 3. Characterisation of degree of heterogeneity across participants (variance across participants, quantified by random effects)
- 4. Identify factors (fixed effects) that predict changes (e.g. compliance score)

Beta estimation will be conducted using maximum likelihood estimation. Following model fitting, residuals will be visualised and qq plots will be generated. If p values are needed for reporting, these will be obtained via Kenward-Roger estimation in the R package lmerTest. A sensitivity analysis will be conducted using either complete case analysis or multiple imputed values

Comparison between sample types may be done via incorporation of data into mixed effects models with an additional covariate (sample type). The sample type with the biggest changes in association with the compliance score may be the most suitable surrogate type for monitoring longitudinal health effects.

Data will be visualised using spaghetti plots, colouring by compliance score and applying facet wraps by sample type.

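### Factors found by looking at change in score may be reported as predictors of change with ordinary p-values in the same women, and the primary analysis is not clearly shielded from the same step

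*SAP*

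**What the plan says.** **Exploration.** Section 6.4.2 states: "Individual slopes for scores will be plotted against covariates". It lists no covariates for this plot and gives no rule for acting on it. The section closes by looking for associations between score changes and clinical or other factors, and in the same sentence adds that "covariate adjustment may be conducted for primary and secondary analyses, where appropriate".

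**Modelling.** Section 6.4.4 states: "Compliance score, sample cell composition, BMI, smoking status, or other factors identified during exploratory data analysis may be used as covariates". Equations 1 and 2 are introduced with "Examples of linear models (covariates may be altered or extended) are provided below". They contain compliance, sample type, BMI or smoking status, cell composition and baseline age as main effects, plus a random time slope per woman. One of four listed uses of the models is "Identify factors (fixed effects) that predict changes (e.g. compliance score". On inference: "If p values are needed for reporting, these will be obtained via Kenward-Roger estimation in the R package lmerTest". Section 6 gives the same route in general terms: "factors may be associated as covariates in mixed-effects models if necessary".

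**Primary analysis.** Section 6.4.3 specifies paired Wilcoxon tests, baseline against month 6, on cervical scores adjusted for immune cell composition. Section 5.4.1 defines success as a significant fall in at least two scores with no significant rise in any.

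**Multiplicity.** Section 5.1 makes correction optional and frames it by outcome, not by candidate predictor.

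**The concern.** A woman's slope is the outcome of interest, her change in score. If a covariate enters the model because it tracked those slopes, and its coefficient is then tested in the same women, the test repeats the look that selected it. Kenward-Roger corrects degrees of freedom and standard errors for small samples. It makes no allowance for selection. The p-value no longer holds the 5% level, and the estimate is biased away from zero.

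Two things are at stake. First, Section 6.4.4 is secondary endpoint reporting, and Section 6.15 requires an exploratory label only for post-hoc, exploratory or unspecified analyses. A data-found factor that Section 6.4.4 already admits could therefore be presented as a planned result. Section 3.6 also says that the study is to supply effect sizes for larger studies, so inflated estimates matter even without p-values.

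Second, the success rule turns on which scores cross p = 0.05. If the adjustment of primary scores can be revisited after associations with change have been seen, a borderline score can move.

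**Working it through.** **1. The plan's own figure.** The SAP gives no error rate for covariate selection. The nearest figure is the sample size in Section 3.6: difference 0.2, SD 0.44, power 0.94, significance level 0.05 (taken as two-sided).

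n = [0.44 × (1.960 + 1.555) / 0.2]² = 59.8, so 60.

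This reproduces the stated 60 as a paired comparison; paired-t power at 60 is 0.934. The checks below use n = 60 and n = 120, the latter being the dietary sub-study.

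**2. Selecting and then testing, when the model tests change.** Assume k candidates, none related to change. The one that best tracks the slopes is picked and tested at 0.05. With independent candidates the chance of p < 0.05 is 1 − 0.95^k. The simulations draw null covariates and test the best one in the same women.

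| k (assumed) | 1 − 0.95^k | Simulated, n = 60 | Simulated, n = 120 | n = 60, candidates correlated 0.3 |
|---|---|---|---|---|
| 1 | 5.0% | 5.1% | 5.0% | – |
| 3 | 14.3% | – | – | – |
| 4 | 18.5% | 19.1% | 18.8% | – |
| 5 | 22.6% | – | – | – |
| 10 | 40.1% | 39.5% | 40.6% | 34.8% |
| 20 | 64.2% | 63.6% | 63.7% | 53.9% |

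These rates are per score and per tissue. A larger sample does not lower them.

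**3. The equations as printed.** They contain (time|id) but no fixed time effect and no time-by-covariate product. A covariate's coefficient therefore describes its association with the level of the score. A simulation with four visits (assumed SDs: intercept 0.4, slope 0.05 per month, residual 0.2) picked the null covariate that best tracked the slopes, for k = 4, 10 and 20:

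- tested against level, as in the printed equations: significant in 5.7%, 7.4% and 7.5% at n = 60, and 5.9%, 6.8% and 8.1% at n = 120;
- tested against change: 18.7%, 40.3% and 64.1% at n = 60;
- one covariate fixed in advance, tested against change: 4.5% to 5.6% over all settings.

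The full inflation thus needs a slope or interaction model. The SAP does not write one, but it permits one, and its aim of finding predictors of change requires one.

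**4. What restores the level.** Bonferroni over every candidate screened gave 4.8% to 5.3% (about 4% with correlation 0.3). Picking in one half of the women and testing in the other gave 4.5% to 5.6%.

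**5. Primary analysis, by comparison of sections.** Section 6.4.3 adjusts for immune cell composition only. Section 6.4.2 allows further adjustment of primary analyses. Section 5.4.1 allows a mixed model with compliance as covariate. The table in Section 6.16 (broken in the text at hand) appears to list under the primary outcome both a paired analysis adjusted for cell composition and a cervical mixed model adjusted also for age and, as examples, BMI and compliance. No section says which of these decides success.

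**The case against.** The strongest reply is that the SAP never calls the slope plot a selection rule. The sentence follows one about the suitability of random intercepts and slopes, so it may be a display step for choosing random effects. Much of the exploration in Section 6.4.2 uses month 0 scores, not change. Sections 2.1, 3.1 and 3.6 describe the study as exploratory and a pilot. Covariates found in exploration, and the p-values themselves, are optional. All of this stands, so the plan permits the circular step but does not prescribe it.

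Four stronger readings are tempting and are not supported:

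- *All predictor p-values in Section 6.4.4 are circular.* The named factors, including compliance, the plan's own example, are fixed in advance. They carry only ordinary multiplicity: four per equation apart from sample type, so 1 − 0.95⁴ = 18.5% if all are null and independent.
- *The 14% to 40% applies to Equations 1 and 2 as written.* It does not (step 3 of the working).
- *Spurious predictors will be carried into follow-on projects.* Section 6.14 sends subsidiary biomarker scores to a hold-out set or to those projects. It says nothing about the predictors of Section 6.4.4.
- *The primary test is undefined.* Section 6.4.3 states it firmly. The gap is that the other sections do not make their adjusted versions subordinate to it.

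The exploratory label does not close the gap. Nothing requires a data-found factor to be marked as such, and neither a correction across candidates nor a hold-out is given for this analysis.

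**Conclusion.** The concern holds as a permitted bias. Sections 6.4.2 and 6.4.4 together allow a factor found through its association with change to be reported as a predictor of change, with a nominal p-value in the same women. For such a factor the p-value is too small and the effect too large; the size of the effect bias was not computed. In a model that tests change, the chance that the best null candidate reaches p < 0.05 is about 14%, 23% and 40% for k = 3, 5 and 10, assuming independent candidates and one score in one tissue. The SAP gives no k, so how often this would happen cannot be said.

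Two linked defects are plain from the text. The printed equations cannot answer the question about predictors of change, and the success rule is not tied to one adjustment of the primary scores. The changes are worth making before analysis, but they do not call the trial's design into question.

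**What to change.** (a) In Section 6.4.4, add to Equations 1 and 2 a fixed time term and time-by-covariate terms for the factors already named (compliance, cell composition, BMI or smoking status, baseline age). Give p-values for predictors of change only for these.

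(b) Report any factor found from the exploration as hypothesis-generating, with its estimate but no p-value. Alternatively, use a permutation test that repeats the whole screening step. That requires a numerical screening rule and a candidate list, because a visual judgement cannot be repeated on permuted data.

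(c) In Section 5.4.1, state that success is judged only on the immune-cell-adjusted paired Wilcoxon tests of Section 6.4.3. State in Sections 6.4.2 and 6.16 that any further covariate adjustment of primary scores, including the mixed-model row of the table, is supportive.

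The cost is SAP wording, plus one permutation routine if that option is taken. No new data or visits are needed. The downside is that fewer post-hoc predictors can be called significant.
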